**10.3.5. Reporting of SAEs****SAE reporting via SAE report**

- Facsimile transmission of the SAE report is the preferred method to transmit this information to the sponsor or designee.
- Initial notification via telephone does not replace the need for the investigator to complete and sign the SAE report within the designated reporting time frames.
- Contacts for SAE reporting can be found in SAE report.

**10.3.6. Regulatory Reporting Requirements****SAE regulatory reporting**

Prompt notification by the investigator to the sponsor of an SAE is essential so that legal obligations and ethical responsibilities toward the safety of participants and the safety of a study intervention under clinical investigation are met.

- The sponsor has a legal responsibility to notify both the local regulatory authority and other regulatory agencies about the safety of a study intervention under clinical investigation. The sponsor will comply with country-specific regulatory requirements relating to safety reporting to the regulatory authority, IRBs/IECs, and investigators.
- An investigator who receives an investigator safety report describing an SAE or other specific safety information (eg, summary or listing of SAEs) from the sponsor will review and then file it along with the IB and will notify the IRB/IEC, if appropriate according to local requirements.

## 10.4. Appendix 4: Contraceptive and Barrier Guidance

### 10.4.1. Definitions

Word/Phrase	Definition
Women of childbearing potential (WOCBP)	
Females are considered a woman of childbearing potential if they have
 
 
had at least 1 cycle of menses, or
 
Tanner 4 breast development.
 
 
Any amount of spotting should be considered menarche. If Tanner Staging of breasts is performed as part of study procedures, please refer to the Reproductive, Pregnancy and Pediatrics Safety Committee Safety Guidance for Children in Clinical Trial regarding Tanner Staging.

Women not of childbearing potential (WNOCBP)	
Females are considered women not of childbearing potential if they
 
 
have a congenital anomaly such as Mullerian agenesis
 
are infertile due to surgical sterilization, or
 
are postmenopausal.
 
 
Examples of surgical sterilization include hysterectomy, bilateral oophorectomy, tubal ligation.

Postmenopausal state	
The postmenopausal state should be defined as:
 
 
1. A woman at any age at least 6 weeks postsurgical bilateral oophorectomy with or without hysterectomy, confirmed by operative note; or
 
2. A woman aged at least 40 years and up to 55 years with an intact uterus, not on hormone therapy*, who has had cessation of menses for at least 12 consecutive months without an alternative medical cause, AND
 
 
With a follicle-stimulating hormone >40 mIU/mL; or
 
 
3. A woman aged 55 or older not on hormone therapy, who has had at least 12 months of spontaneous amenorrhea, or
 
4. A woman aged at least 55 years with a diagnosis of menopause prior to starting hormone replacement therapy
 
 
* Women should not be taking medications during amenorrhea such as oral contraceptives, hormones, gonadotropin-releasing hormone, anti-estrogens, selective estrogen receptor modulators, or chemotherapy that could induce transient amenorrhea.

Reproductive toxicology studies	Embryofetal studies are toxicity studies in pregnant animals designed to identify abnormalities in the development of fetuses, which could indicate potential for teratogenicity in humans. The relevant dosing period is during organogenesis.

### 10.4.2. Contraception Guidance

#### Contraception guidance for females

WOCBP and women not of childbearing potential may participate in this trial.

WOCBP who are completely abstinent as their preferred and usual lifestyle, or in a same-sex relationship as their preferred and usual lifestyle:

Must...	Must not...
agree to either remain abstinent or stay in a same-sex relationship without sexual relationships with males	
 
use periodic abstinence methods 
 
calendar
 
ovulation
 
symptothermal, or
 
post-ovulation
 
 
 
declare abstinence just for the duration of a trial, or
 
use the withdrawal method
 

WOCBPs who are NOT completely abstinent as their preferred and usual lifestyle, or NOT in a same-sex relationship as their preferred and usual lifestyle, must do the following:

Topic	Condition
Pregnancy testing	Have a negative serum test result at screening followed by a negative urine result within 24 hours prior to treatment exposure. See the protocol SoA for subsequent pregnancy testing requirements.
Contraception	Agree to use 2 forms of effective methods of contraception where at least 1 form must be a highly effective method of contraception. These forms of contraception must be used for the duration of the study.

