### 1.3. Schedule of Activities (SoA)

	Screening	Periods 1 and 2 Study Days – at least 35 days washout between Day 1 doses												ED b	Comments
Procedure	D -28 to D -2	D -1 a	D1 a	D2	D3	D4	D5	D6	D7	D8	D15	D21	D36 (±1) a		
Informed consent	X														
Participant admission to CRU		X													
Ethanol and urine drug screen testing	X	X													Per site CRU local requirements
Tirzepatide dosing			0 hour												Study drug will be administered after an overnight fast of at least 8 hours.
Participant discharge from CRU						X									Inpatient stay may be extended at the investigator's discretion for safety monitoring.
Outpatient visit							X	X	X	X	X	X	X		
Medical history and demographics	X														
Physical examination /medical assessment	X		Predose			X							X	X	Full physical examination at screening. Thereafter, assessments performed to include medical review and targeted, symptom-driven examination, as appropriate. Additional assessments may be performed at investigator's clinical discretion.
Weight	X		Predose										X	X	
Height	X														
Temperature	X		Predose												
Safety 12-lead ECG c	X				X									X	
Vital signs (hours)	X		Predose, 12	24	48	72				X	X	X	X	X	Additional unscheduled measures may be taken, at the clinical discretion of the investigator.
Clinical laboratory tests	X		Predose							X			X	X	See Appendix 2 for details. Day 1 predose sample is for baseline only and need not be reviewed prior to first dosing. Performed by local laboratory at screening and central laboratory for subsequent visits.
Pregnancy test	X		Predose										X	X	Female participants only. Serum pregnancy test will be performed at screening and urine pregnancy tests at subsequent visits.
FSH test, if applicable	X														Female participants considered to be postmenopausal only. Women with confirmed nonchildbearing potential status can be exempted from further pregnancy tests during the study after screening.
AEs/concomitant medications	X	X	X	X	X	X	X	X	X	X	X	X	X	X	

	Screening	Periods 1 and 2 Study Days – at least 35 days washout between Day 1 doses												ED b	Comments
Procedure	D -28 to D -2	D -1 a	D1 a	D2	D3	D4	D5	D6	D7	D8	D15	D21	D36 (±1) a		
Pharmacogenetic sample c			Predose												Single sample in Period 1 only.

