Blood glucose monitoring (hours) c			Predose, 12	24, 36	48	72									Performed using a bedside glucose monitor. Additional unscheduled measurements may be taken at the clinical discretion of the investigator.
PK sampling (hours) c			Predose, 8, 12	24, 36	48	72	96	120	144	168	336	480	X	X	

Abbreviations: AE = adverse event; CRU = clinical research unit; D or d = day; ECG = electrocardiogram; ED = early discontinuation; FSH = follicle-stimulating hormone; PK = pharmacokinetic(s).

a Period 2, Day -1 procedures (pregnancy tests) and some Period 2, predose procedures (physical examinations, medical assessments, ethanol and drug screening and clinical laboratory assessments) may be omitted if Period 1, D36 (±1) procedure dates occur within 4 days of Period 2 dosing. Period 2, Day 36 (±1) will also be considered as the final follow-up visit.

b Within 14 days upon confirmation of early discontinuation.

c Predose sample should be collected approximately 2 h prior to dose administration.

Note: All sampling and procedure times are given relative to dosing (Time 0 hour) with tirzepatide (predose or hours postdose). Unless otherwise indicated, predose procedure may be performed any time prior to dosing.

If multiple procedures take place at the same time point, the following order of the procedures should be used: ECGs, vital signs, PK sample (record of actual PK sampling time is the priority), clinical laboratory sample, blood glucose and pharmacogenetic sample.

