**4.1.3. Washout Period**

There will be a washout of at least 35 days between tirzepatide doses.

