### **8.2.9. Pregnancy Testing**

Pregnancy testing will be performed for all female participants at the time points detailed in the SoA (Section 1.3). Serum pregnancy testing will be used at screening. Urine pregnancy testing will be used at all other time points, as per SoA. See Section 8.3.2 for more detail.

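### The protocol does not state one consistent pregnancy-test requirement before the second dose: the SoA row, its footnote a and Section 10.4.2 do not line up

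*Protocol*

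**What the plan says.** Each participant receives two single doses (Protocol Section 6.1). Section 4.1.3 sets a minimum interval but no maximum: "There will be a washout of at least 35 days between tirzepatide doses".

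Four places bear on pregnancy testing before those doses.

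- **Section 10.4.2, guidance for females.** Women of childbearing potential who are not abstinent and not in a same-sex relationship must "Have a negative serum test result at screening followed by a negative urine result within 24 hours prior to treatment exposure". The next sentence reads "See the protocol SoA for subsequent pregnancy testing requirements".
- **Section 1.3, SoA pregnancy-test row.** The test is marked at screening, Day 1 predose, Day 36 (±1) and early discontinuation. Nothing is marked at Day -1. The comment adds: "Serum pregnancy test will be performed at screening and urine pregnancy tests at subsequent visits".
- **Section 1.3, footnote a.** The footnote covers "Period 2, Day -1 procedures (pregnancy tests) and some Period 2, predose procedures". The predose items it names are laboratory assessments, ethanol and drug screens, medical assessments and physical examinations. Its rule is that all of these "may be omitted if Period 1, D36 (±1) procedure dates occur within 4 days of Period 2 dosing".
- **Section 8.2.9.** After the serum test at screening, "Urine pregnancy testing will be used at all other time points, as per SoA".

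**The concern.** Section 7.1 makes pregnancy a reason for permanent discontinuation of study intervention. With two single doses, dose 2 is the only one that can still be withheld once treatment has begun, and the test before dose 2 is the check that would trigger this. Whether that test is required, and how recent it must be, should be clear from the protocol.

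It is not. Section 10.4.2 can be read as requiring a result within 24 hours before each dose, or only before the first. If it means only the first, the SoA must supply the rule for dose 2, and there the row and the footnote disagree about which day the test belongs to. The study is multicenter, so sites could in good faith follow different rules for the same dose.

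**Working it through.** There is no sample-size or power figure to reproduce. The check sets the texts side by side, with a small calculation on the age of the test.

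**Step 1: does Section 10.4.2 cover dose 2?** The wording refers to exposure without naming a period or dose number. Each participant is exposed twice, so the text neither includes nor excludes dose 2 expressly. The reference to the SoA for subsequent tests favours a first-dose reading but does not state it.

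**Step 2: what does the SoA require before dose 2?**

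| Item | Where the SoA row puts it | Where footnote a puts it |
|---|---|---|
| Pregnancy test | Day 1 predose; Day -1 blank | Period 2 Day -1 |
| Ethanol and drug screen | Day -1; Day 1 blank | Period 2 predose |

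The footnote's labels for these two items are the reverse of the rows.

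- *Literal reading:* the footnote waives a Day -1 pregnancy test that the row does not schedule. The Day 1 predose test stands, because pregnancy tests are not among the predose procedures that the footnote lists.
- *Reading by apparent intent:* the labels were swapped, and the footnote waives the Day 1 predose test in Period 2.

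**Step 3: how old can the last test be on the reading by intent?** Inputs: Period 1 final visit on Day 36 ± 1; dose 2 at least 35 days after dose 1, so on Period 1 Day 1 + 35 = Day 36 at the earliest; footnote limit of 4 days = 4 × 24 h = 96 h.

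| Period 1 final visit (test) | Dose 2, in Period 1 days | Approximate age of test | Footnote condition | 24-hour condition, if it covers dose 2 |
|---|---|---|---|---|
| Day 36 | Day 36, after the test | under 24 h | met | met |
| Day 35 | Day 36 | about 24 h | met | depends on clock times |
| Day 36 | Day 40 | 4 × 24 = 96 h | met | missed by about 96 − 24 = 72 h |

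**Step 4: how likely is the gap?** The planned duration of about 14 weeks is consistent with 28 + 35 + 35 = 98 days, which puts Period 2 Day 1 on Period 1 Day 36. On that schedule test and dose can fall on the same day and both conditions are met. Because the washout has no upper limit, later dosing is possible, and footnote a expressly provides for a gap of up to 4 days. The documents give no figure for how often this would happen.

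**The case against.** The strongest reply is that there is no conflict. Section 10.4.2 describes a sequence: serum test at screening, then a urine test shortly before exposure, then the SoA for whatever follows. On that reading the 24 hours belong to dose 1 and the SoA, including footnote a, governs dose 2. Section 8.2.9 also refers tests after screening to the SoA. This is plausible and perhaps the more natural reading. A reader might infer that the protocol imposes two contradictory windows on dose 2; the documents do not establish that. What remains is that the 24-hour condition is not limited to the first dose in words, and that the SoA, if it governs alone, is unclear about the test in question.

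A reader might also see a further competing timing in the SoA note: "Unless otherwise indicated, predose procedure may be performed any time prior to dosing". That does not hold. The note's opening words make it give way to any specific window, and a test done predose on Day 1 is within 24 hours of dosing in any case.

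Nor does the footnote put every woman of childbearing potential outside the 24 hours. That condition applies only to those who are neither abstinent nor in a same-sex relationship, and a same-day test and dose meets it. The footnote is also permissive and presupposes a recent Day 36 test, and Section 10.4.2 separately requires these women to use two forms of contraception throughout the study. These points limit the consequence but do not tell a site which rule to follow.

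**Conclusion.** The point stands as an unreconciled ambiguity. The firmest part is internal to the SoA: the row schedules the pregnancy test at Day 1 predose, and footnote a treats it as a Day -1 procedure, so a site cannot tell whether the Period 2 predose test may be skipped. The second part is conditional. If the footnote is meant to waive that test, dose 2 can follow a result up to about 96 hours old, four times the 24-hour window; this breaches Section 10.4.2 only if that section covers dose 2 and only when dosing follows the visit by more than 24 hours.

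The matter concerns participant safety and uniform conduct across sites. It does not touch the sample size or the bioequivalence analysis. It should be corrected because it decides whether a test is done before the only dose that can still be withheld for pregnancy.

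**What to change.** Reconcile the SoA pregnancy-test row, footnote a and Section 10.4.2 so that all three state the same requirement and the same window for each of the two doses. Section 10.4.2 should say which dose or doses its 24-hour condition covers. Footnote a should name the pregnancy test, and the ethanol and drug screen, under the study day on which the rows schedule them, and should say plainly whether the Period 2 predose pregnancy test is among the procedures that may be omitted. The sponsor decides which window applies; this review takes no position on it.

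The cost is protocol wording and, at most, a urine test that the SoA already schedules. No change to the SAP is needed.

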#### Contraception guidance for males

The following table describes contraception guidance for all men.

Topic	Guidance
For all men	should refrain from sperm donation for the duration of the study and for 90 days
Contraception for men with partners of childbearing potential	
 
either remain abstinent (if this is their preferred and usual lifestyle), or
 
must use condoms during intercourse for the duration of the study, and for 90 days
 

Contraception for men in exclusively same-sex relationships, as their preferred and usual lifestyle	Are not required to use contraception

### Examples of different forms of contraception

Examples of highly effective, effective, and ineffective methods of contraception can be found below.

Methods	Examples
Highly effective contraception (less than 1% failure rate)	
 
• female sterilization
 
• combination oral contraceptive pill
 
• progestin-only contraceptive pill (mini-pill)
 
• implanted contraceptives
 
• injectable contraceptives
 
• contraceptive patch (only women <198 pounds or 90 kg)
 
• vasectomy (if only sexual partner)
 
• fallopian tube implants (if confirmed through hysterosalpingogram)
 
• combined contraceptive vaginal ring, or
 
• intrauterine devices
 

Effective contraception	
 
• male or female condoms with spermicide
 
• diaphragms with spermicide or cervical sponges
 
• barrier method with use of a spermicide 
 
◦ condom with spermicide
 
◦ diaphragm with spermicide, or
 
◦ female condom with spermicide
 
 
 

Ineffective forms of contraception whether used alone or in any combination	
 
• spermicide alone
 
• periodic abstinence
 
• fertility awareness (calendar method, temperature method, cervical mucus, or symptothermal)
 
• withdrawal
 
• postcoital douche, or
 
• lactational amenorrhea
 

## 10.5. Appendix 5: Genetics

### Use/analysis of DNA

- Genetic variation may impact a participant's response to study intervention, susceptibility to, and severity and progression of disease. Variable response to study intervention may be due to genetic determinants that impact drug absorption, distribution, metabolism, and excretion; mechanism of action of the drug; disease etiology; and/or molecular subtype of the disease being treated. Therefore, where local regulations and IRB/IEC allow, a blood sample will be collected for DNA analysis from consenting participants.
- DNA samples will be used for research related to tirzepatide or T2DM and related diseases. They may also be used to develop tests/assays including diagnostic tests related to tirzepatide and T2DM. Genetic research may consist of the analysis of 1 or more candidate genes or the analysis of genetic markers throughout the genome or analysis of the entire genome (as appropriate).
- The samples may be analyzed as part of a multistudy assessment of genetic factors involved in the response to tirzepatide or study interventions of this class to understand study disease or related conditions.
- The results of genetic analyses may be reported in the clinical study report or in a separate study summary.
- The sponsor will store the DNA samples in a secure storage space with adequate measures to protect confidentiality.
- The samples will be retained while research on tirzepatide or T2DM continues but no longer than 15 years or other period as per local requirements.

**10.6. Appendix 6: Medical Device Adverse Events (AEs), Adverse Device Effects (ADEs), Serious Adverse Events (SAEs) and Device Deficiencies: Definition and Procedures for Recording, Evaluating, Follow-up, and Reporting**

Refer to Appendix 3 for definitions and procedures for recording, evaluating, follow-up, and reporting of all events.

## 10.7. Appendix 7: Liver Safety: Suggested Actions and Follow-Up Assessments

### Hepatic evaluation testing

See Section 8.2.8.1 for guidance on appropriate test selection.

Testing by an investigator-designated local laboratory should be performed for all testing defined by this guidance.

The local laboratory must be qualified in accordance with applicable local regulations.

Hepatic Hematology Panel	Hepatic Clinical Chemistry Panel
Hemoglobin	Total bilirubin
Hematocrit	Direct bilirubin
Erythrocytes (RBCs - red blood cells)	Alkaline phosphatase (ALP)
Leukocytes (WBCs - white blood cells)	Alanine aminotransferase (ALT)
Differential:	Aspartate aminotransferase (AST)
Neutrophils, segmented	Gamma-glutamyl transferase (GGT)
Lymphocytes	Creatine kinase (CK)
Monocytes	Other Chemistry
Basophils	Acetaminophen
Eosinophils	Alkaline phosphatase isoenzymes
Platelets	Ceruloplasmin
Cell morphology (RBC and WBC)	Copper
Hepatic Coagulation Panel	Ethyl alcohol (EtOH)
Prothrombin time, INR (PT-INR)	Haptoglobin
Hepatitis A virus (HAV) testing:	Immunoglobulin IgA (quantitative)
HAV total antibody a	Immunoglobulin IgG (quantitative)
HAV IgM antibody	Immunoglobulin IgM (quantitative)
Hepatitis B virus (HBV) testing:	Phosphatidylethanol (PEth) a
Hepatitis B surface antigen (HBsAg)	Urine Chemistry
Hepatitis B surface antibody (anti-HBs)	Drug screen
Hepatitis B core total antibody (anti-HBc)	Ethyl glucuronide (EtG) a
Hepatitis B core IgM antibody	Other Serology
HBV DNA b	Anti-nuclear antibody (ANA)
Hepatitis C virus (HCV) testing:	Anti-smooth muscle antibody (ASMA) c
HCV antibody	Anti-actin antibody d
HCV RNA b	Epstein-Barr virus (EBV) testing:
Hepatitis D virus (HDV) testing:	EBV antibody
HDV antibody	EBV DNA b
Hepatitis E virus (HEV) testing:	Cytomegalovirus (CMV) testing:
HEV IgG antibody	CMV antibody
HEV IgM antibody	CMV DNA b
HEV RNA b	Herpes simplex virus (HSV) testing:
Microbiology	HSV (Type 1 and 2) antibody
Culture:	HSV (Type 1 and 2) DNA b
Blood	Liver kidney microsomal type 1 (LKM-1) antibody
Urine	

a These tests are not done by local laboratory in Singapore.

b Reflex/confirmation dependent on regulatory requirements, testing availability, or both.

c Not required if anti-actin antibody is tested.

d Not required if anti-smooth muscle antibody is tested.

## 10.8. Appendix 8: Pancreatic Monitoring

### Diagnosis of acute pancreatitis

Acute pancreatitis is an AE of interest in all studies with tirzepatide, including this study. The diagnosis of acute pancreatitis requires 2 of the following 3 features (Banks and Freeman 2006; Koizumi et al. 2006):

- abdominal pain, characteristic of acute pancreatitis (ie, epigastric pain radiating to the back, often associated with nausea and vomiting)
- serum amylase (total, pancreatic, or both) and/or lipase  $\geq 3x$  ULN
- characteristic findings of acute pancreatitis on CT scan or magnetic resonance imaging.

If acute pancreatitis is suspected, the investigator should

- obtain appropriate laboratory tests, including pancreatic amylase (p-amylase) and lipase
- perform imaging studies, such as abdominal CT scan with or without contrast, or abdominal magnetic resonance imaging
- evaluate for possible causes of acute pancreatitis, including alcohol use, gallstone/gall bladder disease, hypertriglyceridemia, and concomitant medications.

### Discontinuation for acute pancreatitis

If acute pancreatitis is diagnosed, the participant must discontinue use of the IPs.

### Asymptomatic elevation of serum amylase and/or lipase levels

Serial measures of pancreatic enzymes have limited clinical value for predicting episodes of acute pancreatitis in asymptomatic patients (Nauck 2016; Steinberg et al. 2017a,b). Therefore, further diagnostic follow-up of cases of asymptomatic elevation of pancreatic enzymes (lipase and/or p-amylase  $\geq 3x$  ULN) is not mandated but may be performed based on the investigator's clinical judgment and assessment of the participant's overall clinical condition.

